### 7.2.2 Exclusion Criteria

1. Patient with past medical history or ongoing presence of other types of liver disease including, but not limited to, the following:
  - a) Biliary atresia of any kind
  - b) PFIC
  - c) Benign recurrent intrahepatic cholestasis
  - d) Suspected or proven liver cancer or metastasis to the liver on imaging studies

2. Patient with a past medical history or ongoing presence of any other disease or condition known to interfere with the absorption, distribution, metabolism (specifically bile acid metabolism), or excretion of drugs in the intestine, including but not limited to, inflammatory bowel disease
3. Patient with past medical history or ongoing chronic (i.e. >3 months) diarrhea requiring intravenous fluid or nutritional intervention for treatment of the diarrhea and/or its sequelae
4. Patient has a confirmed past diagnosis of infection with human immunodeficiency virus or other present and active, clinically significant chronic infection
5. Recent infection requiring hospitalization or treatment with parenteral anti-infective within 4 weeks of randomization (Study Day 1) or completion of oral anti-infective treatment within 2 weeks prior to start of Screening Period
6. Cancer within the last 5 years except for basal cell carcinoma
7. Cancer >5 years prior to screening except for non-liver cancers with no evidence of recurrence
8. Chronic kidney disease with an impaired renal function and a glomerular filtration rate <70 mL/min/1.73 m^2
9. Patient with surgical history of disruption of the enterohepatic circulation (biliary diversion surgery) within 6 months prior to start of Screening Period
10. Patient has had a liver transplant or a liver transplant is planned within 6 months of randomization
11. Decompensated liver disease, history or presence of clinically significant ascites, variceal hemorrhage, and/or encephalopathy
12. INR >1.4 (the patient may be treated with Vitamin K intravenously, and if INR is ≤1.4 at resampling the patient may be randomized)
13. Serum ALT >10 × ULN at Screening
14. Serum ALT >15 × ULN at any time point during the last 6 months unless an alternate etiology was confirmed for the elevation
15. Total bilirubin >15 × ULN at Screening
16. Patient suffers from uncontrolled, recalcitrant pruritic condition other than ALGS. Examples include, but not limited to, refractory atopic dermatitis or other primary pruritic skin diseases

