4.8 Safety Analyses

Safety criteria are as follows:

- Primary safety analysis is the incidence of TEAEs and TEAEs categorized by causality, severity, and seriousness assessments made by the investigator by comparing active arms vs. placebo. This includes liver-related mortality and liver decompensation events (protocol Section 10.2.2.3) and all-cause mortality.
- Safety will also be evaluated by the following assessments:
 - Physical examinations
 - Concomitant medications
 - Vital signs
 - Laboratory test results (including clinical chemistry, hematology, urinalysis, AFP, vitamins A and E, 25-hydroxy vitamin D, and INR)
 - Abdominal ultrasound
 - Discontinuations due to AEs

All safety analyses will be performed on the SAF unless otherwise specified, using the following common rules:

- The analysis of the safety variables will be analyzed using descriptive statistics and summaries by treatment group for each cohort.
- No inferential statistical analysis will be planned.
- For each safety variable, the last value collected prior to first dose of study drug will be used as the baseline for all analyses.

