4.8.1 Adverse Events

General common rules for summarizing adverse events

All AEs will be classified by SOC and PT using the MedDRA version 25.0.

AEs will be classified as TEAEs, defined as follows: An AE (classified by preferred term) that occurs during the Treatment Period will be considered a TEAE if it has a start date on or after the first dose date of study drug, or it has a start date before the date of the first dose date of study drug but worsened in severity on or after the date of the first dose date of study drug.

AEs with missing start dates, but with stop dates either overlapping with the treatment period or missing, will be considered TEAEs. A TEAE with missing drug-relationship will be considered as related. A TEAE with missing severity will be considered as CTCAE grade 3 (severe). Details for imputing missing or partial start dates of adverse events are described in [Appendix 5](#). AEs with the same AE reference number that is collected on AE page of eCRF are counted as one AE only.

Adverse events of interest (AEIs)

Adverse events of interest (AEIs) will be selected for analyses as indicated in [Table 6 - Selections for AEIs](#).

Table 6 – Selections for AEIs

AEIs	Selection
Liver Decompensation	
a. The following TEAEs will be included:
 
PT = International normalised ratio increased and checkbox that event is refractory to vitamin supplementation is checked and at least 1 INR value (within 2 weeks [+/-] of the AE started date) is >1.5
 
PT = Vitamin K increased and checkbox that event is refractory to vitamin supplementation is checked and at least 1 INR value (within 2 weeks [+/-] of the AE started date and checkbox) is >1.5
 
PT = Hepatic failure, Acute on chronic liver failure, or Subacute hepatic failure
 
b. The following TEAEs occurring as separate events or in the presence of (i.e. ongoing medical history or AE) PT of portal hypertension and/or PT of hepatic cirrhosis were included:
 
PT = Ascites
 
PT = Hepatorenal syndrome
 
PT = Portopulmonary hypertension
 
PT = Oesophageal varices haemorrhage
 
PT = Gastric varices haemorrhage
 
PT = Intestinal varices haemorrhage
 
PT = Hepatic encephalopathy

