Summary tables for number of patients with any TEAEs by SOC and PT by severity (grade 1 to grade 5) and by causality (related [possibly, probably, and definitely] vs unrelated [unlikely and unrelated]), will also be provided. AEs with the worst severity will be used in the by-severity summaries. Similarly, AEs with the worst causality (most related to treatment) will be used in the by-causality summaries. If severity or causality is missing, data will be imputed as grade 3 or related, respectively.

When a patient has the same adverse event, based on preferred terminology, reported multiple times during the study, the patient will only be counted once at the preferred terminology level in adverse event frequency tables. Where a patient has multiple adverse events within the same SOC during the study, the patient will only be counted once at the SOC level in adverse event frequency tables. In the AE summaries, AEs will be sorted by alphabetically for SOC and PT.

In addition to the frequency summary of TEAE tables, the exposure adjusted incidence rate (EAIR) (per 100 patient years at risk) with the 95% confidence interval, based on Poisson distribution, will also be provided for each of the following AE tables:

- TEAEs by SOC and PT
- Liver-related TEAEs by SOC and PT
- Liver Decompensation TEAEs (as defined in [Table 6 - Selections for AEs, for TEAEs listed in b in the presence of \(i.e. ongoing medical history or AE\) PT of portal hypertension and/or PT of hepatic cirrhosis](#)) by SOC and PT
- FSV Deficiency refractory to clinically recommended vitamin supplementation TEAEs by SOC and PT
- Possible Sequelae of FSV Deficiency TEAEs by SOC and PT
- Clinically Significant Diarrhea TEAEs by SOC and PT

The EAIR (per 100 patient years at risk) will be calculated as follows:

$$\text{Number of subjects with event} / \text{Total cumulative time at risk (years)} \times 100$$

where total cumulative time at risk is the sum of individual time at risk. The time at risk for a subject with the event of interest will be calculated (in years) as:

$$(\text{first event date} - \text{date of first dose} + 1) / 365.25$$

The time at risk for a subject without the event of interest is calculated as:

$$(\text{last participation date} - \text{date of first dose} + 1) / 365.25$$

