Kaplan-Meier curves may be used for time to event data (time to first liver decompensation TEAEs [as defined in [Table 6 - Selections for AEs, for TEAEs listed in b in the presence of \(i.e. ongoing medical history or AE\) PT of portal hypertension and/or PT of hepatic cirrhosis](#)] onset (days), time to first liver-related TEAEs onset (days), time to first FSV deficiency refractory to clinically recommended vitamin supplementation TEAEs onset (days), time to first possible sequelae of FSV deficiency TEAEs onset (days), time to first clinically significant diarrhea event onset (days), and time to all-cause mortality (weeks)). Patient will be censored at the last contact date if no event occurs.

A diarrhea event is defined as a TEAE with PT as Diarrhoea or Diarrhoea haemorrhagic. Descriptive summary statistics will be used to summarize the duration of each diarrhea episodes (days), the number of episodes per patient and time to onset of diarrhea (days). In addition, the summaries will be provided for clinically significant diarrhea TEAEs.

In order to assess who developed onset of FSV Deficiency refractory to clinically recommended vitamin supplementation, a listing merging with concomitant medications and selected lab data will be provided.

Analysis of special situations

Certain safety events are defined by regulatory authorities as Special Situations and require reporting. These Special Situations include:

- Overdose of study medication
- Suspected abuse/misuse of study medication
- Medication error involving the study medication
- Drug-drug interaction
- Pregnancy

Special Situations should be reported on the Special Situations page of eCRF, whether or not they result in an AE/SAE. Number (%) of patients experiencing these special situations will be provided.

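### The composite liver decompensation rate and its optional Kaplan-Meier curve use only the narrower of the two counts that the SAP's frequency tables report side by side

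*SAP*

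**What the plan says.** SAP 4.8.1, Table 6, defines the liver decompensation event of interest in two parts.

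- **Part a** carries no background condition. It covers the liver failure terms ("PT = Hepatic failure, Acute on chronic liver failure, or Subacute hepatic failure") and INR or vitamin K terms that are refractory to supplementation with an INR above 1.5.
- **Part b** is worded "The following TEAEs occurring as separate events or in the presence of (i.e. ongoing medical history or AE) PT of portal hypertension" and/or hepatic cirrhosis. Its event terms are ascites, hepatorenal syndrome, portopulmonary hypertension, three variceal bleeding terms (for example "PT = Oesophageal varices haemorrhage") and hepatic encephalopathy.

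SAP 4.8.1 then uses part b as follows.

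- The TEAE overview has one line for part b events occurring separately and one for those with the background term.
- The SOC and preferred-term frequency tables have the same pair.
- The EAIR list has a single liver decompensation entry: "Table 6 - Selections for AEs, for TEAEs listed in b in the presence of" portal hypertension and/or cirrhosis.
- The Kaplan-Meier paragraph lists "time to first liver decompensation TEAEs" with the same restriction. It says only that such curves may be used.

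In the EAIR, a patient without a qualifying event contributes time up to the last participation date. In the Kaplan-Meier analysis that patient is censored at last contact. SAP 4.8 places "liver decompensation events (protocol Section 10.2.2.3) and all-cause mortality" within the primary safety analysis, which it defines as the incidence of TEAEs, and plans no inferential safety analysis.

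**The concern.** The two outputs that summarise liver decompensation as a composite over follow-up time leave out part of the definition in Table 6, and the SAP does not say why. Suppose a child has a first ascites or encephalopathy event, neither portal hypertension nor cirrhosis recorded as ongoing history or AE, and no part a event. The frequency table would show a liver decompensation event, while the EAIR table under the same label could read zero. Within an arm, the narrow count can equal the broad one or fall below it, but cannot exceed it.

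No other Table 6 category is cut back in this way. Liver-related events, fat-soluble vitamin deficiency, its possible sequelae and clinically significant diarrhoea all enter the EAIR and Kaplan-Meier lists as Table 6 defines them. Few events can be expected among 45 patients over 24 weeks, so a single event decides whether the composite rate is zero.

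**Working it through.** The documents give no liver decompensation rate to reproduce. The check has two parts.

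**1. Where each count is used (SAP 4.8.1)**

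| Output | Part b as separate events | Part b with background term |
|---|---|---|
| TEAE overview | yes | yes |
| SOC/PT frequency tables | yes | yes |
| Composite liver decompensation EAIR | no | yes |
| Kaplan-Meier, time to first event (optional) | no | yes |
| All-TEAE frequency tables and EAIR by SOC and PT | each event under its own term | each event under its own term |

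Separate events could mean all part b events, or only those without a background term. On either reading, the EAIR and the curve lack the events without a background term.

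**2. What one such patient does to the composite EAIR**

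Inputs from the documents: 45 patients randomised 2:1 (SAP 2.1), hence 30 and 15; 24 weeks = 168 days (SAP 1.1); the EAIR formula and its stop at the first event (SAP 4.8.1).

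Assumptions: no dropout; onset at day 84; neither background term recorded; no part a event. Follow-up is 168 days, or 196 days if every patient attended the safety follow-up visit (day 196, protocol Table 1). Intervals are exact Poisson.

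Formula: EAIR = 100 × patients with event ÷ total years at risk.

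*As written.* The patient is not counted and contributes full time.
- Odevixibat: 30 × 168 ÷ 365.25 = 13.80 years; EAIR 0 (95% CI 0 to 26.7).
- Placebo: 15 × 168 ÷ 365.25 = 6.90 years; EAIR 0 (0 to 53.5).

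*Counted broadly.* The patient's time stops at day 84.
- Odevixibat: (29 × 168 + 84) ÷ 365.25 = 13.57 years; 100 × 1 ÷ 13.57 = **7.4** (0.2 to 41.1).
- Placebo: (14 × 168 + 84) ÷ 365.25 = 6.67 years; 100 × 1 ÷ 6.67 = **15.0** (0.4 to 83.5).

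*With 196 days of follow-up.*
- Odevixibat: (29 × 196 + 84) ÷ 365.25 = 15.79 years; 100 × 1 ÷ 15.79 = **6.3** (0.2 to 35.3), against 0 (0 to 22.9) as written.

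With two or three such patients on odevixibat at 168 days, the broad rate is 15.0 (1.8 to 54.2) or 22.9 (4.7 to 66.9). As written it stays at 0. Dropout, planned at about 20%, would shorten time at risk and so raise the contribution of each event.

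**The case against.** **Nothing is hidden.** A reader might infer that such an event counts as no event in the report. It does not. It appears in the broad line of the overview, in the broad SOC/PT table and in the all-TEAE, severity and causality tables. It also has an EAIR with confidence interval under its own preferred term, because the EAIR list begins with all TEAEs by SOC and PT. The gap is one composite EAIR entry and one optional curve. This stands in full.

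**The primary safety analysis is intact.** A reader might infer that it is undercounted. It is the incidence of TEAEs, and those tables carry both counts. The EAIR is an addition to them. This also stands.

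**The broad count is not shown to be the right one.** Protocol exclusion 11 reads "Decompensated liver disease, history or presence of clinically significant ascites, variceal hemorrhage, and/or encephalopathy", with no portal hypertension or cirrhosis condition, and it is tempting to use it as the benchmark. But it is an eligibility screen and has its own clinical-significance qualifier. For the event itself, SAP 4.8 points to protocol 10.2.2.3, which refers to protocol Table 5, where the criteria are redacted. Protocol 5.2 reports cardiac defects in about 90% of patients and renal abnormalities in 74%, so asking for a hepatic background before counting a term such as ascites is a defensible choice for specificity. SAP Table 1 also records that Table 6 was updated after FDA comments, which are not available here. The case for replacing the narrow count therefore fails.

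**Site coding.** Nothing in the documents supports saying that the count depends on sites' coding habits. The SAP applies MedDRA 25.0 and does not say that sites code, and the background term may come from ongoing history or from an AE.

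One point is left unanswered: the SAP reports both counts in one set of tables and only one in the next, without a reason. Rates for single preferred terms do not replace the composite.

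**Conclusion.** The inconsistency is real and minor. The composite liver decompensation EAIR, and the Kaplan-Meier curve if it is produced, can show no event where the broad frequency table shows one. For one affected patient the composite rate is 0 rather than about 7.4 per 100 patient-years on odevixibat (6.3 with 196 days of follow-up) or about 15.0 on placebo. These figures rest on 30 and 15 patients, no dropout and onset at day 84. They illustrate the mechanism and do not predict events. The intervals with and without the event overlap widely, so one event says little about the underlying rate.

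Any effect on the comparison between arms could go either way. Efficacy inference and type I error are not affected. The documents do not support going further and calling the narrow count an error.

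**What to change.** In the EAIR list of SAP 4.8.1, add a second liver decompensation entry covering part a plus all part b events, with or without the background term. In the Kaplan-Meier paragraph, add the matching curve if the narrow curve is produced. Keep the narrow count in both places with its present standing, as the frequency tables already do. Spell out the broad entry as part a plus all part b, so that the reading of separate events cannot change the count.

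If the sponsor prefers to leave the lists as they are, a sentence giving the reason for using only the narrow count would be the minimum.

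The cost is SAP wording before database lock and one extra run of existing programs, with no new data. The drawback is a less specific composite that may include events of non-hepatic cause, which is why the two should stand side by side.

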4.8.2 Additional Safety Assessments

4.8.2.1 Laboratory Variables

The following laboratory variables will be analyzed.

- Hematology:
 - Red blood cells and platelets: hemoglobin, hematocrit, red blood cell count, and platelet count
 - White blood cells: white blood cell count, neutrophils, lymphocytes, monocytes, basophils, and eosinophils
- Clinical chemistry:
 - Metabolism: total cholesterol, triglycerides, creatine kinase, albumin
 - Electrolytes: sodium, potassium, chloride, calcium
 - Renal function: creatinine, blood urea nitrogen, estimated glomerular filtration rate
 - Liver function: ALT, AST, Alkaline phosphatase (and isoenzymes as applicable), direct bilirubin, total bilirubin, gamma-glutamyl transferase
 - Pregnancy test: Serum β -human chorionic gonadotropin (all female patients with positive urine pregnancy test)
- Urinalysis:
 - Urinalysis for quantitative analysis: pH, proteins, glucose, blood, ketones, leukocytes, and nitrites
- Other Labs: Vitamin A and E, 25-hydroxy vitamin D, INR, Alfa-fetoprotein (AFP), and Prothrombin Time

Quantitative analyses

For all laboratory variables above, descriptive statistics for clinical laboratory values (in SI units for all tests, and in conventional units for selected tests (Appendix 8) and absolute changes from baseline at each post-baseline visit (Appendix 3) will be presented. The change to the last visit will also be summarized. Central laboratory data will be used for the summary. If central laboratory data are not available due to COVID-19 or other reasons, local laboratory data will be used if available.

Figure for ALT, AST, total bilirubin, ALP, and gamma-glutamyl transferase will be presented as individual patient trellis plot over time.

Analyses according to reference normal range

Shift tables from baseline to the highest and lowest post-baseline value for quantitative variables will be presented for the clinical laboratory parameters. The laboratory results will be classified as low, normal, and high based on the normal range that provided by central/local laboratories.

For ALT, AST and total bilirubin, a shift table based on the following classifications (per DILI guidance and CTCAE) will be presented:

[figure not shown]
- ALT and AST: ≤ 3 ULN, > 3 and ≤ 5 ULN, > 5 and ≤ 10 ULN, > 10 ULN
- Total Bilirubin: ≤ 2 ULN and > 2 ULN

Liver monitoring

A listing of patients meeting the criteria for liver monitoring (Table 7) will be provided.

Table 7 – Liver monitoring

Laboratory value(s) or Symptoms	Criterion
AST or ALT in combination with total bilirubin (confirmed with repeat testing within 48 to 72 hours)	CCI
Total bilirubin (confirmed with repeat testing within 48 to 72 hours)	
INR	

Laboratory value(s) or Symptoms	Criterion
Symptoms	
Symptoms	

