Other features associated with ALGS include failure to thrive, short stature, immunodeficiency with recurrent infections, pancreatic insufficiency, delayed puberty, and developmental delays [Diaz-Frias 2019]. The clinical presentation of ALGS is extremely variable and even patients from the same family with the same genetic mutation may have different presentations [Kamath 2003].

Approximately 95% of patients with ALGS present with chronic cholestasis, usually within the first 3 months of life [Emerick 2002]. Laboratory evaluation of these patients revealed elevated serum bile acids, elevated liver function tests (LFTs), and conjugated hyperbilirubinemia. Associated symptoms include xanthomas, growth failure, and pruritus.

The majority (45% to 88%) of patients with ALGS present with severe, intractable pruritus, which can be disabling. Patients with ALGS and their caregivers confirm that pruritus is the most bothersome symptom [Kamath 2018].

Currently, there is no approved medical therapy for the treatment of ALGS.

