4.3 Demographics and Baseline Characteristics, Prior or Concomitant Medications

Demographics, baseline and disease characteristics

The following demographics, baseline and disease characteristics, medical and surgical history will be summarized using descriptive statistics in the FAS.

Demographic, baseline, and disease characteristics

- Age in years as quantitative variable and Age in years as categorical variables (Age group 1: 0 to <10, 10 to <18; Age group 2: 0 to <2, 2 to <12, 12 to <18) based on actual age.
- Age group (0 to <10, 10 to <18) from IWRS for randomization
- Gender (Male, Female)
- Race (American Indian or Alaska Native, Asian, Black or African American, Native Hawaiian or Other Pacific, Islander, White, Other, Not reported)
- Race group (White, Non-White (including race as not reported))
- Ethnicity (Hispanic or Latino, Not Hispanic or Latino, Not reported)
- Ethnicity group (Hispanic or Latino (including ethnicity as not reported), Not Hispanic or Latino)
- Country and region ([Appendix 4](#))
- Use of ursodeoxycholic acid (UDCA)
- Use of anti-pruritus medication
- Baseline values: height (or length depending on age), weight as quantitative and categorical (≤ 10 and > 10 kg) variable, body mass index (BMI), Z-score (height, weight, and BMI), pruritus score (i.e., AM, PM, average AM and PM scratching score from ObsRO), serum bile acid as quantitative and categorical (\geq median and $<$ median based on overall randomization population) variable, estimated glomerular filtration rate (eGFR), ALT, AST, gamma-glutamyl transferase (GGT), total bilirubin, direct bilirubin as quantitative and categorical (> 3 and ≤ 3 mg/dL), alkaline phosphatase (ALP), INR, cholesterol, triglycerides, vitamin A, vitamin E, and 25-hydroxy vitamin D.
- Disease characteristics include
 - Genetic testing results for ALGS if performed at screening (e.g., mutation in *JAG1* vs *NOTCH2*; per protocol, testing is only performed at screening if not available in the patient's medical record), years since ALGS diagnosis
 - Child-Pugh classification (mild (Class A), moderate (Class B), or severe hepatic impairment (Class C)), and hepatic impairment classification (no impairment, mild, moderate, or severe) per NCI Organ Dysfunction Working Group [6]. Details of the classification are described in [Appendix 9](#).

eGFR will be calculated based on the modified/bedside Schwartz equation. The values of eGFR will be provided by the central laboratory vendor.

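### The total bilirubin shift table stops at 2 x ULN while entry is allowed up to 15 x ULN, so it cannot show worsening in a patient who starts above 2 x ULN

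*SAP*

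**What the plan says.** SAP 4.8.2.1 states, for ALT, AST and total bilirubin, that "a shift table based on the following classifications (per DILI guidance and CTCAE) will be presented". The classes are "ALT and AST: ≤ 3 ULN, > 3 and ≤ 5 ULN, > 5 and ≤ 10 ULN, > 10 ULN" for the transaminases and "Total Bilirubin: ≤ 2 ULN and > 2 ULN" for bilirubin.

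The same section plans a general shift table for laboratory parameters: "The laboratory results will be classified as low, normal, and high based on the normal range that provided by central/local laboratories".

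On entry, Protocol 7.2.2 excludes "Total bilirubin >15 × ULN at Screening" and "Serum ALT >10 × ULN at Screening". It sets no limit on AST.

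On the expected population, Protocol 5.2 says of patients with chronic cholestasis: "Laboratory evaluation of these patients revealed elevated serum bile acids, elevated liver function tests (LFTs), and conjugated hyperbilirubinemia". SAP Appendix 9 defines severe hepatic impairment as total bilirubin above 3 x ULN. SAP 4.3 lists that classification among the baseline characteristics, and SAP 4.5.3 and 4.6.3 use it for subgroups. SAP 4.3 also summarises "direct bilirubin as quantitative and categorical", with a split at 3 mg/dL.

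**The concern.** A shift table counts, by arm, the patients who moved to a worse class. It can do this only if a worse class exists above the baseline class. For total bilirubin the top class begins at 2 x ULN, in a cholestatic disease where much higher values are admissible at entry. The SAP therefore describes baseline bilirubin in finer bands (Appendix 9) than it uses to count deterioration on treatment.

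The trial interrupts drug on liver criteria that include total bilirubin alone (Protocol Table 5) and has a hepatic adjudication committee (Protocol 11.2.4). About 30 patients will be on odevixibat and 15 on placebo (45 split 2:1). A by-arm hepatic table with no cell for worsening among patients with raised baselines could be misread as reassuring.

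**Working it through.** The plan states no figure to reproduce here. The check is to place values in the planned classes.

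**Inputs.** Bilirubin cut: 2 x ULN (SAP 4.8.2.1). Bilirubin entry ceiling: 15 x ULN (Protocol 7.2.2, exclusion 15). ALT cuts: 3, 5 and 10 x ULN (SAP 4.8.2.1). ALT entry ceiling: 10 x ULN (Protocol 7.2.2, exclusion 13). Safety baseline: last value before first dose (SAP 4.8). The fold-rises are assumed, for illustration.

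**Step 1: total bilirubin in the planned classes (multiples of ULN).**

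| Baseline | Rise | Post-baseline | Cell |
|---|---|---|---|
| 1.5 | 2-fold | 3 | ≤2 to >2: counted |
| 2 | 1.5-fold | 3 | ≤2 to >2: counted |
| 3 | 3-fold | 9 | >2 to >2: no shift |
| 5 | 3-fold | 15 | >2 to >2: no shift |
| 7.5 | 3-fold | 22.5 | >2 to >2: no shift |
| 15 | 3-fold | 45 | >2 to >2: no shift |

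For any baseline b > 2 and any rise r > 1, b × r > 2, so the class never changes. The share of such rises that are counted is 0%, whatever their size. A fall to 2 x ULN or below is counted.

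**Step 2: the low/normal/high table.** A baseline above 2 x ULN is already high, and a rise stays high. This table does not fill the gap.

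**Step 3: contrast with ALT.** The top ALT cut equals the ALT entry ceiling. Rises from 4 to 8, 6 to 12 and 10 to 20 x ULN all change class.

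**Step 4: are such patients expected?** The planned class above 3 x ULN lies wholly inside the blind range. The direct bilirubin split points the same way, given an assumption: since total is at least direct, direct above 3 mg/dL means total above 2 x ULN whenever the ULN for total bilirubin is below 3 / 2 = 1.5 mg/dL. The documents do not give the ULN. Neither fact says how many patients there will be.

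**Step 5: extent.** The blind part of the entry scale is 15 − 2 = 13 of 15 multiples, 13/15 = 87%. This is a share of the scale, not of patients.

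**Step 6: what added cuts would do.** Take cuts at 2, 5, 10 and 15 x ULN and baselines spread evenly over >2 to 15 (an assumption, width 13).

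- 1.5-fold rise: no change of class for baselines in (2, 3.33] and (5, 6.67], width 1.33 + 1.67 = 3.0. Counted: 1 − 3.0/13 = 77%.
- 2-fold rise: no change for (2, 2.5], width 0.5. Counted: 1 − 0.5/13 = 96%.
- 3-fold rise: 2 × 3 = 6 already exceeds 5, so 100% are counted.

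**The case against.** The strongest reply is that the same data appear in several other planned outputs.

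- Change-from-baseline summaries by visit include the maximum (SAP 4.1, 4.8.2.1), so a rise from 3 to 14 x ULN could appear as its arm's largest change.
- Listings are sorted by treatment group (SAP 4.1), so with 45 patients arm counts can be read off the liver-monitoring listing.
- An MMRM of change in total bilirubin is planned (SAP 4.6.4.1), as are individual trellis plots.
- Liver-related adverse events are counted by arm, with exposure-adjusted rates (SAP 4.8.1).
- The DSMB sees unblinded liver values about quarterly (Protocol 11.2.3).

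Much of this stands. A reader might infer that bilirubin worsening would go unseen in this trial; the documents do not support that. Each output still differs from the missing count. A maximum shows one patient and is not tied to baseline level. The MMRM estimates mean change. Trellis plots are individual displays. The listing's thresholds are redacted, so its coverage cannot be judged either way. A laboratory rise becomes an adverse event only through the investigator's judgement of clinical significance (Protocol 10.1.2.2). Protocol 11.2.2.8 also plans counts of potentially clinically significant laboratory values, but SAP 4.8.2.1 neither carries these forward nor defines thresholds; whether they were dropped is a separate question.

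Two further limits hold. The SAP attributes its classes to outside guidance whose bilirubin grades are not in the documents, so no claim is made that the classes depart from it. And safety analysis is descriptive only, so no formal test is affected.

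**Conclusion.** The point holds for the shift tables. For a patient with baseline total bilirubin above 2 x ULN, neither table can show deterioration, and no other planned output is a by-arm count of laboratory bilirubin worsening from a raised baseline. For baselines at or below 2 x ULN, the two-class table can still show worsening.

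The size in patients cannot be computed. It is tempting to read the 87% as a share of patients, or to multiply 45 by a guessed proportion; with no baseline bilirubin distribution in the documents, neither is supported. It is also tempting to say that both transaminases have classes reaching their entry limit, but only ALT has an entry limit.

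This is a modest reporting gap. It does not touch the primary or key secondary conclusions.

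**What to change.** In SAP 4.8.2.1, do one or both of the following:

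1. Add total bilirubin classes above 2 x ULN that span the permitted entry range, for example cuts at 5, 10 and 15 x ULN. The exact cuts are for the sponsor.
2. Add, by arm, the number of patients whose highest post-baseline total bilirubin reaches stated multiples of their own baseline (for example 1.5 and 2 times).

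The second option avoids the dependence on where a baseline falls within a class, and needs few cells. These are reporting categories only; they leave eligibility, liver monitoring and treatment rules unchanged.

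Cost: SAP wording and table shells, using data already collected. The downside is a wider table with small cells: five bilirubin classes give 5 × 5 = 25 cells for about 15 placebo patients.
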